### **10.5.1.3 Other safety data**

The other secondary safety objectives of the study will be based on sexual and neuropsychological development data.

The age when patients reach each Tanner Stage II-V will be summarized on the FAS Puberty of the studies CRADM2305 and TOSCA.

The following variables will be summarized on the Safety Set (SS) (those are only collected in the CRAD001M2305 study) using descriptive statistics:

- age when females will start thelarche
- age when females will have their first menses
- age when males will reach adrenarche

For the age at which Tanner Stage II will be achieved, summary statistics from the Kaplan-Meier distribution will be determined on the FAS puberty, including the median age and the proportions of patients reaching this milestone at some given ages. These statistics will be given as point estimates with 95% confidence intervals. The same analyses will be performed for the following variables: age at which each Tanner Stage III, IV and V will be reached. Age at thelarche (females), age at menarche (females) and age at adrenarche (males) will be described similarly on the SS.

Potential delayed puberty will be defined based on Tanner stage and also on onset of menarche for girls. Potential cases identified through this algorithm, will be then clinically reviewed by assessing all available information in order to conclude the clinical relevance of the delay.

Potential delayed puberty in girls is defined as failure to attain Tanner Stage II (for both breast development and pubic hair) by age 13, or absence of menarche by age 15 or within 5 years of attainment of Tanner Stage II ([Fenichel 2012](#)) Potential delayed puberty in boys is defined as failure to attain Tanner Stage II (for both testis and pubic hair) by age 14 ([Traggiai 2002](#), [Tanner 1962](#))

Rates of potential delayed puberty will be described for boys and girls separately among the patients at risk of delayed puberty along with 95% confidence intervals. The patients at risk are patients who may potentially present an event of potential delayed puberty at baseline.

The rates of potential delayed puberty will be described in the different subgroups defined by duration of everolimus exposure. These subgroups will be defined in the Report and Analysis Plan.

The duration of exposure and the age at start of everolimus will be summarized using descriptive statistics in the subgroup of patients with potential delayed puberty.

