3.6 Study treatment

For CRAD001M2305 patients, all data described below will be pooled with the corresponding data from Study CRAD001M2301 and will be summarized using the safety set.

The participation in this study does not require the administration of everolimus. In such cases in which the patient was taking everolimus, data collection (such as therapeutic drug trough level, duration of everolimus interruptions and everolimus prescribed dose) will only be recorded, when available.

For patients in Study CRAD001M2305, the duration of everolimus exposure and cumulative everolimus dose will be described using descriptive statistics on the Safety Set.

The total duration of everolimus exposure will be calculated as the total duration of everolimus exposure received while on Study CRAD001M2301 plus the total duration of (commercially supplied) everolimus exposure reported in Study CRAD001M2305.

Similarly, the cumulative dose of everolimus will be calculated as the cumulative everolimus dose received while on Study CRAD001M2301 plus the cumulative everolimus (commercially supplied) dose reported in Study CRAD001M2305.

All exposure data will be listed.

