The age category immediately above the patient's exact age should be used. SDS is actually a Z score that measures the distance from the population mean in units of standard deviations. That is, $SDS < 0$ refers to values lower than the population mean, and for example $SDS \leq -1.645$ refers to values in the lowest 5%. (The usual percentile more commonly used in the clinical practice can be derived from the Z-score by a normal distribution).

The time-course of height and BMI SDS will be summarized, side by side, on the FAS of the studies CRAD001M2305 and TOSCA using descriptive statistics by year since the enrollment date (for TOSCA patients) or since the start of everolimus (for CRAD001M2305 patients). The counts and frequencies of patients with height and BMI SDS values lower than the 5th percentile (notably low) or higher than the 95th percentile (notably high) will be described on the FAS, overall and by region. The counts and frequencies by region will be provided if sufficient sample size observed within the region for CRAD001M2305 study.

The rate of height (respectively BMI) growth notable abnormality will be calculated as the rate of patients with a height $SDS < 5$ th percentile at the last time point where height is reported.

If the number of CRAD001M2305 patients is sufficient and if a high rate of notably height (respectively BMI) growth abnormality occurs, the relationship between the everolimus exposure and the height growth abnormality will be further explored as detailed below:

- The rate of height (respectively BMI) growth abnormality will be described in the different subgroups defined by the duration of everolimus exposure. These subgroups are described in the Section 3.12.
- The duration of exposure and the age at start of everolimus will be summarized using descriptive statistics in the subgroups of patients with and without a height (respectively BMI) growth abnormality.
- A logistic regression including the duration of exposure and the age at the start of everolimus as continuous covariates will also be used to further explore the relationship between the everolimus exposure and the height (respectively BMI) growth notable abnormality. Additional covariates (e.g. time normalized Cmin) might also be included in the model.

In addition, individual patient graphs for height and BMI over time will be provided for CRAD001M2305 patients.

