3.8.2 Tanner Stage

For CRAD001M2305 patients, all data described below will be pooled with the corresponding data from Study CRAD001M2301.

Tanner Stage will include two components for boys (testis and pubic hair) and two components for girls (breast development and pubic hair).

Percentage of patients who will have reached Tanner Stage V by age 16 (for females) or age 17 (for males) will be provided, side by side, on the FAS Puberty of the studies CRAD001M2305 and TOSCA, along with 95% confidence intervals.

If the number of CRAD001M2305 patients is sufficient and notably high abnormality, the relationship between the everolimus exposure and the Tanner Stage will be further explored as detailed below:

- The percentage of patients who will have reached Tanner Stage V by age 16 (for females) or age 17 (for males) will be described in the different subgroups defined by duration of everolimus exposure. These subgroups are described in the Section 3.12.
- The duration of exposure and the age at start of everolimus will be summarized using descriptive statistics in the subgroups of patients who will reach and who will not reach Tanner Stage V by age 16 (for females) or age 17 (for males).
- A logistic regression including the duration of exposure and the age at the start of everolimus as continuous covariates may also be used to further explore if needed the relationship between the everolimus exposure and the achievement of Tanner Stage V by age 16 (for females) or age 17 (for males). Additional covariates (e.g. time normalized C_{min}) might also be included in the model.

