If the number of patients in CRAD001M2305 is sufficient, the rates of potential delayed puberty will be described in the different subgroups defined by duration of everolimus exposure. These subgroups are described in the Section 3.12.

If a high rate of potential delayed puberty occurs and if the number of patients in the CRAD001M2305 study is sufficient, the duration of exposure and the age at start of everolimus will be summarized using descriptive statistics in the subgroup of patients with potential delayed puberty.

If a high rate of potential delayed puberty occurs and if the number of patients in each study is sufficient, a logistic regression including the duration of exposure and the age at the start of everolimus as continuous covariates will also be used to further explore the relationship between the everolimus exposure and the rate of potential delayed puberty. Additional covariates (e.g. time normalized Cmin) might also be included in the model.

These patients will be clinically reviewed by assessing all available information in order to evaluate their puberty development.

All responses to the individual questions from the TAND Checklist will be summarized using descriptive statistics on both studies, side by side, and over time on the FAS of studies CRAD001M2305 and TOSCA (Research Project 4).

All the responses are categorical in nature from the TAND Checklist, if applicable, the frequency of baseline and worst-post baseline will be summarized on both studies, side by side, and over time on the FAS of studies CRAD001M2305 and TOSCA (Research Project 4).

Safety data from other assessments will be listed, notable values flagged, and any other information collected will be listed as appropriate.

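### The table of exposure and age at start for potential delayed puberty covers delayed patients only, so on its own it cannot show a relation to everolimus

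*SAP*

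**What the plan says.** SAP 3.9.2 plans three steps linking potential delayed puberty to everolimus.

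- **Rates by duration.** If numbers are sufficient, "the rates of potential delayed puberty will be described in the different subgroups defined by duration of everolimus exposure".
- **Exposure and age at start.** If the rate is high and numbers are sufficient, these two variables are "summarized using descriptive statistics in the subgroup of patients with potential delayed puberty". No second group is named.
- **Regression.** If the rate is high and numbers are sufficient in each study, "a logistic regression including the duration of exposure and the age at the start of everolimus as continuous covariates will also be used".

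Protocol 10.5.1.3 restricts the second step in the same way but attaches no condition, in a sentence on pubertal delay that begins "The duration of exposure and the age at start of everolimus will be summarized using descriptive statistics in the subgroup of patients with potential delayed".

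The equivalent tables for the other outcomes name both groups. For growth, SAP 3.8.1 has "in the subgroups of patients with and without a height (respectively BMI) growth abnormality". For sexual maturation, SAP 3.8.2 has "descriptive statistics in the subgroups of patients who will reach and who will not reach Tanner Stage V". Both are also conditional in the SAP. Neither document gives a reason for treating delayed puberty differently.

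**The concern.** A mean or median age at start among delayed patients has no meaning for causation or association until it is set beside the value in patients who could have been delayed and were not. The same holds for duration of exposure.

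The plan itself picks out age at start and duration as the two covariates for this outcome. Protocol 2.1 justifies the cohort partly by the young age at which many patients were first exposed, and protocol 1.1.3 gives puberty onset as a reason for the study. If the table is produced as written, it will list the characteristics of a few delayed patients, and readers may be tempted to take a low age at start or a long exposure as a signal when it is simply typical of the cohort.

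**Working it through.** The point rests on wording, so the plan has no figure to reproduce. The check has three parts.

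**1. What a delayed-only table can show.** Assume 15 at-risk patients, of whom 3 are delayed, with exposures of 9, 11 and 12 years. The table reports a median of 11 years. Consider three possible sets of exposures for the 12 non-delayed patients:

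| Non-delayed exposures (years, assumed) | Median | Delayed minus non-delayed |
|---|---|---|
| 3, 4, 4, 5, 5, 6, 6, 7, 7, 8, 8, 9 | 6 | 11 − 6 = +5 |
| 8, 9, 9, 10, 10, 11, 11, 11, 12, 12, 12, 13 | 11 | 11 − 11 = 0 |
| 12, 12, 13, 13, 13, 14, 14, 14, 14, 15, 15, 15 | 14 | 11 − 14 = −3 |

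The planned table is identical in all three cases. The same reasoning applies to age at start.

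**2. What else in the plan supplies the contrast.**

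| Planned output | Uses non-delayed patients? | Duration or trough level? | Age at start? |
|---|---|---|---|
| Rates among patients at risk, by sex (SAP 3.9.2) | Yes, in the denominator | No | No |
| Rates by duration group (SAP 3.9.2, 3.12), if numbers sufficient | Yes | Duration | No |
| Rates by time-normalised Cmin (SAP 3.10), if rate high and numbers sufficient | Yes | Trough level | No |
| Exposure summary on the Safety Set (SAP 3.6) | Yes, not split by delayed status | Duration and dose, no contrast | No |
| Baseline age on the FAS (SAP 3.2, with baseline as in 2.1.4) | Yes, not split by delayed status | No | Close to age at start, no contrast |
| Logistic regression (SAP 3.9.2), if rate high and numbers sufficient in each study | Yes | Duration | Yes |

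Only the last row sets age at start against delayed status.

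**3. Whether that regression is usable.** SAP 4.2 gives 15 patients. The number delayed is not given, so take d = 1 to 5 as an assumption. With two covariates, events per covariate = d / 2:

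- d = 1: 0.5
- d = 2: 1.0
- d = 3: 1.5
- d = 4: 2.0
- d = 5: 2.5

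Some of the 15 may not be at risk; that leaves fewer patients to fit the model. The terms high rate and sufficient number are not defined. SAP 4.2 calls 15 patients too small for any comparison; it says so about the indirect comparison, but the remark suggests how a sufficiency condition is likely to be judged.

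**The case against.** Several counter-arguments have force.

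- **The table may never be produced.** In the SAP it depends on a high rate and on sufficient numbers, and 15 patients may fail that test. This stands. It would be wrong to write as though the table is certain to appear. The protocol version, however, is unconditional, and when numbers are too few for a model, a two-group description is the natural fallback.
- **It may be intended as case description.** SAP 3.8.1 and 3.8.2 introduce their tables as exploring a relationship. In 3.9.2 that word is attached to the regression, and potential cases also go to clinical review. The difference may therefore be deliberate. Even so, the table sits between two steps that examine exposure, and a reader will want to use it that way.
- **A reader might infer that the plan ignores non-delayed patients or has no analysis relating everolimus to delayed puberty.** The documents do not support that. Non-delayed patients enter the rates, the duration groups, the Cmin split and the regression. For the whole cohort, "the duration of everolimus exposure and cumulative everolimus dose will be described using descriptive statistics on the Safety Set", and baseline age is summarised too. Exposure, demographic and safety data are listed, so with 15 patients the contrast could be rebuilt by hand.
- **Whole-cohort values already serve as a reference.** Only partly. They include the delayed patients themselves and patients not at risk. Anyone who started everolimus after passing the milestones cannot become a case, which pulls the reference age at start upward.
- **The outcome is not a listed endpoint.** Correct: potential delayed puberty appears under other safety data, not among the primary or secondary endpoints of protocol section 3. SAP 3.8.2 does plan an age-at-start contrast for Stage V, conditionally. This limits the weight of the point.

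**Conclusion.** The point holds for this one table. As written, it cannot show a relation between potential delayed puberty and either duration of exposure or age at start. For duration, other planned outputs partly fill the gap if their conditions are met. For age at start, nothing does except a conditional regression that is unlikely to be usable with 15 patients.

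The importance is low. The analysis is secondary and descriptive, no test of any rate is planned (SAP 2.4.2.1), and no stated figure changes. A comparison of a few delayed patients with the rest would describe the cohort and would not support inference. The number of cases, the exposures and the number at risk used above are all assumptions; the count of 15 comes from SAP 4.2. That a one-group table shows no contrast does not depend on any of them.

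**What to change.** In SAP 3.9.2, change the population of this summary to *the subgroups of at-risk patients with and without potential delayed puberty*, in line with 3.8.1 and 3.8.2.

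State who counts as without. Only patients followed long enough for the algorithm to classify them should be in that column; those who leave before the relevant age or milestone should be shown separately. This matters because participation ends at Tanner Stage V, so a girl could complete the study before age 15 without menarche and remain unclassified on that criterion.

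A split by sex should not be required. Neither 3.8.1 nor 3.8.2 splits these tables by sex, and dividing, for example, 3 cases gives cells of 3 and 0 or 2 and 1. Showing individual values with sex marked is enough.

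The cost is a few words in the SAP, one added column and a line for unclassified patients. No new data are needed and no other analysis changes.

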## **10.2 Patient demographics/other baseline characteristics**

Demographic and other baseline characteristics will be described by study (CRAD001M2305 and TOSCA), side by side, on the two Full Analysis Sets (FAS and FAS-Puberty).

The baseline value will be the last available assessment on or before the start of everolimus for CRAD001M2305 patients and the first available assessment after the enrollment date for the TOSCA patients.

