2.1.4 Baseline

For CRAD001M2305 patients, the baseline value will be the last available assessment on or before the start of everolimus in the parent study CRAD001M2301.

For the TOSCA patients, the baseline value is taken from the first available assessment on or after the enrollment date.

If patients have no value as defined above, the baseline value will be missing.

2.1.5 First available assessment of endocrine test and Tanner Staging for the CRAD001M2305 patients

The original protocol of the parent study CRAD001M2301 did not require collection of the endocrine blood test nor the Tanner Staging data. These assessments were added in the protocol amendment 2 of CRAD001M2301 and required to be collected during screening and at certain frequency during follow-up. As per the CRAD001M2301 protocol, patients who were ongoing at the time protocol amendment 2 was approved should have the endocrine blood tests and Tanner Staging assessed at their next scheduled visit (considered baseline).

Therefore, some CRAD001M2305 patients who were already enrolled into the parent study CRAD001M2301 before the protocol amendment 2 do not have the endocrine blood test nor the Tanner Staging data on or before the start of everolimus in the parent study, and the first available assessments after the protocol amendment 2 of CRAD001M2301 were considered as the baseline data for those patients in the parent study as well as in the CRAD001M2305 study.

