2.2 Data included in the analysis

This Study CRAD001M2305 is a long-term safety follow-up study and statistical analyses will be primarily descriptive for all endpoints. The planned statistical analysis is described in Section 10 of the protocol.

Data collected for the patients enrolled in this CRAD001M2305 study will be pooled with the corresponding data previously collected in the parent CRAD001M2301 study for the same patients, in particular, background information on the disease history, demographics and baseline characteristics, everolimus exposure, sexual and growth development data. This pooling will allow for the following:

- Obtaining baseline values collected in CRAD001M2301 before start of everolimus
- Calculating the whole exposure to everolimus for patients enrolled in the CRAD001M2305 study
- Considering the whole growth/development course over time from the start of everolimus.

The descriptive analyses of data from the CRAD001M2305 study and TOSCA registry will be presented, side by side, whenever similar data are collected in both studies. This is intended to facilitate the interpretation of the CRAD001M2305 results and help describe any potential impact of everolimus on growth and sexual development, in the TSC population, whose growth and sexual development independent of exposure to systemic mTOR inhibitors is not well characterized.

Table 2-2 summarizes the data which will be included in all the analyses described in the SAP.

Table 2-2 Data included in each analysis

Endpoints	Studies			Analysis Set
	CRAD001M2305	CRAD001M2301	TOSCA	
Baseline characteristics	X	X	X	FAS and FAS Puberty
Patient disposition	X			FAS
Protocol deviations	X			FAS
Concomitant therapy	X	X		Safety Set
Height and BMI	X	X	X	FAS
Tanner stage	X	X	X	FAS puberty
Endocrines	X	X	X	FAS
Adverse events	X	X		Safety Set
Age at menarche	X	X		Safety Set
Age at thelarche	X	X		Safety Set
Age at adrenarche	X	X		Safety Set
Potential delayed puberty	X	X		Safety Set
TAND checklist	X		X	FAS
Indirect comparison	X	X	X	FAS and FAS puberty

Endpoints	Studies			Analysis Set
	CRAD001M2305	CRAD001M2301	TOSCA	
Treatment exposure	X	X		Safety Set
Pharmacokinetics	X	X		Safety Set

In order to ensure all data in the trial is captured, the cut-off date for final analysis will be fixed to the date of the last patient last visit. For the purpose of the final analysis, all tables, figures and listings (TFLs) described in this SAP as well as in TFL shells will be produced.

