3.9.2 Other safety data

For CRAD001M2305 patients, all data described below will be pooled with the corresponding data from Study CRAD001M2301 **except** for the TAND checklist as this assessment was not collected in the parent study CRAD001M2301.

The other secondary objectives of the study will be based on sexual and neuropsychological (TAND checklist) development data.

The age when patients reach each Tanner Stage II-V will be summarized on the FAS Puberty of Studies CRAD001M2305 and TOSCA.

The following variables will be summarized on the Safety Set (those are only collected in the CRAD001M2305 study) using descriptive statistics:

- age when females will start thelarche
- age when females will have their first menses
- age when males will reach adrenarche

For the age at which Tanner Stage II will be achieved, summary statistics from the KM distribution will be determined on the FAS puberty, including the median age and the proportions of patients reaching this milestone at some given ages. These statistics will be given as point estimates with 95% confidence intervals. The same analyses will be performed for the following variables: age at which each Tanner Stage III, IV and V will be reached. Age at thelarche (females), age at menarche (females) and age at adrenarche (males) will be described similarly on the SS.

Potential delayed puberty will be defined based on Tanner stage and also on onset of menarche for girls. Potential cases identified through this algorithm, will be then clinically reviewed by assessing all available information in order to conclude the clinical relevance of the delay.

Potential delayed puberty in girls is defined as failure to attain Tanner Stage II (for both breast development and pubic hair) by age 13, or absence of menarche by age 15 or within 5 years of attainment of Tanner Stage II [Fenichel 2012] Potential delayed puberty in boys is defined as failure to attain Tanner Stage II (for both testis and pubic hair) by age 14 ([Traggiai 2002], [Tanner 1962])

Rates of potential delayed puberty will be described for boys and girls separately among the patients at risk of delayed puberty along with 95% confidence intervals. The patients at risk are patients who may potentially present an event of potential delayed puberty at baseline.

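### As the SAP defines baseline, no M2305 patient (0 of 15) can have a TAND baseline, so the M2305 baseline column of one descriptive TAND table will be empty

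*SAP*

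**What the plan says.** SAP 3.9.2 describes two TAND outputs on the Full Analysis Set, each showing M2305 beside TOSCA (Research Project 4). The first summarises all individual responses over time. The second is conditional: "if applicable, the frequency of baseline and worst-post baseline will be summarized on both studies, side by side, and over time".

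The rules that decide what counts as baseline are elsewhere:

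- SAP 2.1.4, M2305 patients: "the baseline value will be the last available assessment on or before the start of everolimus in the parent study CRAD001M2301".
- SAP 2.1.4, no qualifying value: "If patients have no value as defined above, the baseline value will be missing".
- SAP 2.1.4, TOSCA patients: "the baseline value is taken from the first available assessment on or after the enrollment date".
- SAP 2.1.5 departs from this rule for two kinds of data, named in its title: "First available assessment of endocrine test and Tanner Staging for the CRAD001M2305 patients".
- SAP 3.9.2 pools M2305 with M2301 data, with an exception "for the TAND checklist as this assessment was not collected in the parent study CRAD001M2301". The TAND row of Table 2-2 likewise has marks under M2305 and TOSCA but not under M2301.

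In the protocol, neuropsychological development by TAND is a secondary objective, and Section 3 times the endpoint from M2305 enrolment. Table 7-1 schedules the checklist at Day 1, at the first annual visit and annually after that.

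**The concern.** The baseline rule looks back to the start of everolimus in a study that did not use this instrument. The M2305 half of the baseline display then has nothing to show, while the TOSCA half can be filled wherever the registry holds a first checklist.

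There is a second consequence. If everything after the 2.1.4 baseline point is post-baseline, the M2305 enrolment checklist enters the worst post-baseline value, but the first TOSCA checklist does not enter the corresponding TOSCA value. The two columns would then be built differently although they are printed next to each other.

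At stake is whether this table can be read at all for M2305. Unless the rule is settled beforehand, the choice is between printing an all-missing column and picking a baseline after the data have been seen.

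**Working it through.** The plan states no count of TAND baselines, so there is no figure to reproduce. The check applies the rules in sequence.

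**Inputs**

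| Input | Value | Source |
|---|---|---|
| Start of everolimus, S | first non-zero dose in M2301 | SAP 2.1.1 |
| Exposure before M2305 | all enrolled patients were exposed in M2301 | SAP 2.3.2 |
| TAND checklists in M2301 | none | SAP 3.9.2, Table 2-2 |
| Earliest scheduled M2305 checklist | Day 1/enrolment, E | Protocol Table 7-1 |
| Exceptions to the rule | endocrine tests, Tanner staging | SAP 2.1.5 |
| M2305 patients | 15 | SAP 4.2 |

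**Step 1: does any checklist qualify as baseline?** SAP 2.1.4 requires checklist date ≤ S. Every patient started everolimus in M2301, so S < E. Every M2305 checklist is dated E or later, hence after S. The number of qualifying checklists per patient is 0. The gap between S and E does not matter: assumed gaps of 0.5, 1, 3 and 5 years all give 0.

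**Step 2: what happens then?** The missing-value sentence in 2.1.4 applies, and 2.1.5 does not lift it for TAND. Patients with a TAND baseline: 0/15 = 0%. Patients with it missing: 15/15 = 100%. The percentages are the same for any number of patients.

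**Step 3: how is the first checklist classified in each study?**

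| | M2305 | TOSCA |
|---|---|---|
| First checklist | after S, so post-baseline by inference | baseline |
| Later checklists | post-baseline | post-baseline |

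The M2305 entry in the first row is an inference, because the SAP does not define post-baseline for TAND. For one M2305 patient, adding the Day 1 checklist to the set from which the worst value is taken can only leave that value unchanged or make it worse. The net effect between the studies cannot be derived. It depends on how many checklists each patient has, and the documents do not give this for either study.

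**Step 4: what would an enrolment-based rule give?** If baseline is the first checklist on or after M2305 enrolment, up to 15/15 = 100% of patients could have one. The documents do not report how many checklists were completed, so the possible range is 0 to 15.

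**The case against.** The strongest reply is that the intended meaning can be recovered. SAP 3.9.2 keeps TAND out of the M2301 pooling, SAP 2.3.2 refers to an M2305 baseline when defining the Safety Set, the protocol times the TAND endpoint from enrolment, and Table 7-1 has a Day 1 checklist. All of this points to enrolment. As an account of what was probably meant, that stands. But 2.3.2 neither defines its baseline nor applies it to TAND, and 2.1.4 contains an explicit rule with an explicit consequence. The words "if applicable" in SAP 3.9.2 permit the table to be dropped, but they do not supply a baseline.

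The objection on weight also stands. The table is conditional, descriptive and untested, it has 15 M2305 patients, and the over-time summary still carries their enrolment responses.

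Several stronger readings are tempting, but the documents do not support them:

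- *The protocol also sets the TAND baseline to missing.* Protocol 10.2 does say "The baseline value will be the last available assessment on or before the start of everolimus for CRAD001M2305 patients", but it has no clause making the value missing otherwise, and it stands under demographics and other baseline characteristics.
- *The protocol contradicts itself on a Day 1 checklist.* Sections 4.1 and 7.2.2.5 mention only annual visits, and 7.1.1.1 does not list TAND. But 7.1.1.1 refers to Table 7-1 for details, and annual wording in this protocol does not exclude enrolment. Section 7.2.2.1 calls height and weight annual, yet 7.1.1.1 requires both at enrolment. Section 4.1 puts the hormone sample at annual visits, yet 7.2.2.3 adds Day 1. The text sections are less complete than the table; they do not conflict with it.
- *The worst-value column is biased against everolimus.* Step 3 of the working gives a direction within a patient, not between studies.
- *TOSCA patients have usable baselines and repeats.* The number of Research Project 4 patients with a first or repeated checklist is not given.

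**Conclusion.** The point holds as a minor defect in the SAP. Read as written, 2.1.4 leaves 0 of 15 M2305 patients with a TAND baseline, so the M2305 baseline column of the baseline and worst post-baseline table is empty. By the same reading, the Day 1 checklist becomes post-baseline while the first TOSCA checklist is baseline.

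The zero rests on no modelling assumption, only on the SAP's own statements about the baseline rule, exposure in M2301 and TAND collection. The classification of the Day 1 checklist rests on the inference that post-baseline means after the 2.1.4 baseline point.

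A reader might infer that the TAND objective cannot be met. It can: the over-time summary needs no baseline and follows the protocol endpoint. The damage is limited to one table, and any distortion of its worst-value column cannot be sized from the documents.

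**What to change.** Add to SAP 2.1.5, before the table is produced:

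- The M2305 TAND baseline is the first available checklist on or after M2305 enrolment (scheduled at Day 1 in protocol Table 7-1), which is the rule already used for TOSCA. The table labels it as taken after the start of everolimus.
- Post-baseline for TAND means any checklist after that one, in both studies.

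Using the first available checklist, and not strictly Day 1, also covers a patient whose Day 1 checklist is absent. The rule agrees with the protocol's time origin for this endpoint. A row giving the number of checklists per patient by study would help the reader but is optional.

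The cost is one or two sentences and a table label, with no new data. There are two drawbacks. The M2305 baseline is not a pre-treatment value, so the table cannot show change since everolimus was started. A patient with a single checklist will have a baseline but no post-baseline value.
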